EudraCT	European drug regulatory affairs Clinical Trials
ICU	Intensive Care Unit
IGJ	Inspectie Gezondheidszorg en Jeugd
iMCQ	iMTA Medical Consumption Questionnaire
iMTA	Institute for Medical Technology
iPCQ	iMTA Productivity Cost Questionnaire
LVEF	Left Ventricular Ejection Fraction
MAP	Mean Arterial Pressure
METC	Medical research ethics committee (MREC); in Dutch: medisch-ethische toetsingscommissie (METC)
NSTEMI	Non ST-Elevated Myocardial infarction
QALY	Quality Adjusted Life Year
QOL	Quality Of Life
(S)AE	(Serious) Adverse Event
Sponsor	The sponsor is the party that commissions the organisation or performance of the research, for example a pharmaceutical company, academic hospital, scientific organisation or investigator. A party that provides funding for a study but does not commission it is not regarded as the sponsor, but referred to as a subsidising party.
STEMI	ST-Elevated Myocardial Infarction
WMO	Medical Research Involving Human Subjects Act; in Dutch: Wet Medisch-wetenschappelijk Onderzoek met Mensen

SUMMARY

Rationale: Pump failure due to acute myocardial infarction (AMI) can lead to cardiogenic shock (CS): a state of low blood flow to end-organs with subsequent multi-organ failure that is associated with high mortality rates. The first line pharmacologic treatment strategy in CS is noradrenaline. This vasopressor drug is used to maintain adequate blood pressure. The current guidelines have a weak recommendation for targeting a mean arterial blood pressure (MAP) of ≥ 65 mmHg in order to improve flow and thereby tissue perfusion of the myocardium, kidneys and other organs. However, there is no evidence that an increase in MAP, if achieved by noradrenaline, leads to higher end-organ blood flow and better outcomes. As a matter of fact, the use of noradrenaline may compromise myocardial blood flow in this condition and thus lead to infarct size expansion and worse clinical outcome.

Objective: With this study we aim to investigate the (cost-)effectiveness of reduced noradrenaline in patients with CS by using a lower MAP-target of ≥ 55 mmHg, compared to standard care (target-MAP usually ≥ 65 mmHg). We hypothesize that reduced use of noradrenaline will improve overall survival and decrease renal failure requiring renal replacement therapy.

Study design: Open label, randomized controlled multicenter trial

Study population: Adults patients with CS due to AMI

Intervention: Treatment strategy of reduced noradrenaline use, by means of a lower MAP-target regimen (≥ 55 mmHg).

Main study parameters/endpoints: Primary endpoint: composite of all-cause mortality and severe renal failure leading to renal replacement therapy within 30-days after randomization. Secondary endpoints: duration of catecholamine therapy, enzymatic infarct size, hemodynamic parameters, length of stay in hospital and Intensive Care Units (ICU), quality of life (QOL).

Nature and extent of the burden and risks associated with participation, benefit and group relatedness: In this study no new or additional medication is registered to patients when compared to routine care. This means that all potential risks originate from using a lower MAP-target and reduced use of noradrenaline. In both index and reference group, renal and cerebral functions will be closely monitored.

A potential benefit from study participation is that less exposure to noradrenaline leads to less frequent occurrence of side effects, such as (supra-)ventricular arrhythmias.

The follow-up moments are at 30-days, 3-month, 6-month and 1-year after randomization. These are all part of routine care. At follow-up information on organ function (blood test, ECG, echocardiography) will be gathered, as part of routine care. Additionally, patients will be asked to fill in a questionnaire at 30-days, 3-months, 6-months and 1-year after randomization.

1. INTRODUCTION AND RATIONALE

Yearly, around 6000 patients in the Netherlands suffer from cardiogenic shock (CS) due to acute myocardial infarction (AMI) and this number will only increase, based on demographic developments.[1] Despite efforts to improve survival mortality in CS is as high as 50% and the only evidence based therapy is early revascularization. [2-5] CS after AMI results from the loss of myocardial cells due to ischemia. The poor pumping function of the heart leads to a state with low blood flow to end-organs resulting in multi-organ failure and high mortality rates. Renal failure (and subsequent renal replacement therapy) occurs due to decreased perfusion of the kidneys and is a surrogate marker for end-organ perfusion and a strong predictor for death in CS.[6]

The first-line pharmacologic strategy in CS is noradrenaline, as recommended by current scientific statements.[2, 7] Noradrenaline is a vasopressor drug routinely used in the treatment of CS, under the assumption that a higher mean arterial blood pressure (MAP) will improve myocardial and other end-organ (e.g. renal) perfusion. However, there is no evidence that noradrenaline use and higher blood pressures improve patient outcomes. Firstly, pharmacologically induced improvement of blood pressure has not been associated with better survival. Secondly, there is no evidence that an increase in MAP, if achieved by noradrenaline, leads to greater myocardial and other end-organ blood flow. As a matter of fact, its vasoconstrictive properties reduce flow to the microcirculation of the myocardium and organs, as can be frequently seen by discolouring of skin in patients treated with noradrenaline.[8, 9] And lastly, noradrenaline is associated with adverse events such as (supra-)ventricular arrhythmias that reduce the efficacy of the myocardial pumping function and increase the myocardial oxygen demand. This can lead to expansion of infarct size and worsening of the heart muscle function.

The current, scientifically weak recommendation for noradrenaline (Class IIb) is based on one study that compared noradrenaline with dopamine in a population with all types of shock.[10] The overall trial was neutral and only in a small CS subgroup a trend was reported towards lower 28-day mortality and less arrhythmias in patients treated with noradrenaline, as compared to dopamine. However, there are serious methodological concerns as randomization was not stratified and the test for subgroup differences suggests that the effect was likely based on chance. Furthermore, the comparator group was treated with dopamine, which is known for adverse events such as arrhythmias. In light of the aforementioned limitations, the optimal first-line treatment and MAP-target in patients with CS remains unclear.

Based on the results of a recently published trial (permissive hypotension [lower MAP-target] in patients with vasodilatory hypotension), we anticipate that accepting a lower MAP will lead to a significantly reduced exposure to noradrenaline in the index group. Moreover, in this recent study, no differences were found in fluid balance or use of other vasopressor/inotropic drugs, compared to standard care (noradrenaline use and MAP-target left at discretion of treating physician).[11]

2. OBJECTIVES

Primary objective:

The primary objective of this study is to test whether a treatment strategy with reduced use of noradrenaline in patients with cardiogenic shock is superior to standard care in terms of combined all-cause mortality and renal failure at 30 days.

Secondary objective:

The secondary objectives of this study are to test the following hypotheses:

- Does a treatment strategy with reduced use of noradrenaline in patients with cardiogenic shock lead to lower all-cause mortality at 30 days?
- Does a treatment strategy with reduced use of noradrenaline in patients with cardiogenic shock lead to reduced cardiovascular death at 1 year?
- Does a treatment strategy with reduced use of noradrenaline in patients with cardiogenic shock lead to an increase of days alive and out of hospital at 30 days?

3. STUDY DESIGN

An open label, multicenter randomized controlled trial to ensure level 1 evidence for superiority of the intervention. The standardcare arm will provide a reliable basis for the cost-effectiveness analysis. Patients will be randomly assigned (1:1) to the index regimen (lower MAP-target of ≥ 55 mmHg) or reference regimen (standard MAP-target of ≥ 65 mmHg). Inclusion is estimated to take three years (36 months).

[figure not shown]

Figure 1.

4. STUDY POPULATION

4.1 Population (base)

The study consists of consecutive adult patients with acute myocardial infarction with cardiogenic shock, treated with early revascularization by PCI.

4.2 Screening

Screening for eligibility takes place at the emergency department, the catheterization laboratory or at the intensive care unit (ICU) / coronary care unit (CCU).

4.3 Inclusion criteria

In order to be eligible to participate in this study, a subject must meet all of the following criteria:

1. Acute myocardial infarction, STEMI or NSTEMI
2. Cardiogenic shock, characterized by:
 - I. Signs of impaired organ perfusion with at least one of the following criteria:
 - a. Altered mental status
 - b. Cold, clammy skin and extremities
 - c. Oliguria with urine output < 30ml/hour
 - d. Serum lactate > 2.0 mmol/L
 - II.
 - a. Systolic blood pressure (SBP) < 90 mmHg for > 30 minutes, OR
 - b. Use of drugs to maintain SBP > 90 mmHg at presentation before randomization.
 - III. Signs of pulmonary congestion

4.4 Exclusion criteria

A potential subject who meets any of the following criteria is excluded from participation in this study:

- Resuscitation > 30 minutes
- Mechanical cause of cardiogenic shock (e.g. papillary muscle rupture, ventricular septal rupture)

- Onset of shock > 12 hours
- Imminent need for mechanical circulatory support

5. TREATMENT AND FOLLOW-UP

5.1 Randomization and treatment allocation

Patients are randomized either at the catheterization laboratory (before or after revascularization by PCI) or at the ICU / CCU up to a maximum of 2 hours after PCI, as soon as the treating physician has established the diagnosis of CS (*see criteria above*). As patients are in immediate need of treatment with noradrenaline, patients are randomized without preceding informed consent (*see section 5.6*).

Patients meeting the selection criteria are randomized in a 1:1 ratio to index regimen, with a MAP-target of ≥ 55 mmHg, or reference regimen, with a standard MAP-target. A web based randomization program with stratification per center is used. The randomized regimen is started immediately after randomization.

5.2 Index regimen with a lower MAP-target (≥ 55 mmHg)

Noradrenaline therapy (dosage and duration) is given with a target MAP of ≥ 55 mmHg.

- If a patient is not on vasoactive drugs at the moment of randomization, noradrenaline is only started when the MAP is < 55 mmHg. Noradrenaline is titrated in accordance with local protocols until the MAP-target of ≥ 55 mmHg has been reached.
- If a patient is on noradrenaline or other vasoactive drugs, treatment is reduced or discontinued when the MAP is consistently ≥ 55 mmHg.
- If, after an initial treatment period with noradrenaline, the target MAP of ≥ 55 mmHg is maintained without any medical intervention, no active blood pressure lowering medication is required.

Blood pressure is continuously monitored by an intra-arterial catheter which is placed according to clinical routine.

5.3 Reference regimen with a standard MAP-target (usually ≥ 65 mmHg)

Noradrenaline therapy (dosage and duration) is given according to standard of care.

- If a patient is on noradrenaline or other vasoactive drugs at the moment of randomization, treatment is continued in accordance with usual care with a standard MAP-target.
- If a patient is not on noradrenaline or other vasoactive medication at the moment of randomization, noradrenaline is started in accordance with local routine.

Blood pressure is continuously monitored by an intra-arterial catheter which is placed according to clinical routine.

5.4 Use of co-interventions

The use of other vasoactive medication is allowed under strict regulations. Patients need to have some sign of clinical deterioration, e.g. a decrease in urinary output, mottling of the skin or an altered mental status. This observation should be confirmed biochemically by measurement of lactate. If lactate is ≥ 2 mmol/L or higher than baseline measurement, patients are observed 2-4 hours before lactate measurement is repeated. If lactate fails to drop after this observational period, a hemodynamic profile is obtained, preferably via a pulmonary artery catheter. If invasive hemodynamic measurement indicates a poor cardiac output, physicians may consider adding inotropes. If lactate still fails to drop with this new strategy, further treatment is left at the discretion of the treating physician. This includes letting go of the MAP-target and starting any medication. The steps mentioned above are summarized in **figure 2**.

The use of mechanical circulatory support devices, such as Impella, IABP and ECMO, is allowed under strict criteria when bail-out therapy is necessary. That is when medical therapy fails (persistently high lactate, poor cardiac output) despite treatment according to the medical guidance protocol (usually on very high vasoactive treatment).

5.5 Follow-up

Patients are clinically followed until hospital discharge. Thereafter they are contacted by telephone at 30 days after randomization for assessment of neurological outcome. Questionnaires on resource utilization and on quality of life are distributed at 30 days, 3, 6 and 12 months after randomization. Information about hospital readmissions until one year is obtained. Furthermore, outcomes of diagnostic information of the routinely scheduled visit to the outpatient clinic is collected (including findings from functional imaging of the heart).

Medical guidance protocol in case of clinical deterioration

[figure not shown]

Figure 2.

5.6 Informed consent

5.6.1 Informed consent of a legal representative

As patients are incapacitated and legally incompetent at randomization and at the implementation of the randomized regimen assignment, legal representatives are approached to ask for consent as soon as they are available.

Legal representatives are informed of enrollment of the patient in the trial. If the legal representative(s) gives informed consent, treatment according to allocation is continued. If the legal representative(s) need more time to think, treatment according to allocation is continued until the legal representative(s) decides whether to give consent or not. The assent will be recorded in the patient notes.

If the legal representative(s) objects to treatment according to allocation and therefore does not sign the written informed consent form, patients will be treated in accordance with standard practice. This means that treatment continues in the same manner in case of allocation to reference treatment. If a patient was allocated to receive index treatment, they will be treated according to standard practice thereafter.

In case the family declines consent, but the patient survives, informed consent for further participation (questionnaires, interview by phone) and to use patient data will be asked from the patient once he or she regains consciousness. For safety reasons, if the legal representative(s) declines informed consent and the patient dies, data on the primary endpoint will still be collected (mortality, renal replacement therapy).

All information is also provided in writing.

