5.6.2 Informed consent from the patient

As soon as patients have recovered, information about enrollment in the study is provided to the patient. They are explained that a legal representative has been informed about enrollment in the study.

Patients are explained that information about the clinical course until one year is needed for the study. The patients are also invited to receive a telephone call at 30 days and to fill-out questionnaires on quality of life and work resumption, via e-mail or surface mail.

Patients are asked to sign a written informed consent stating that they agree to fill out questionnaires on quality of life and work resumption (if applicable) and that clinical

information about follow-up beyond hospital discharge is gathered from hospital and general practitioners records. If the patient refuses, no further information beyond hospital discharge is collected. Patients are allowed to discontinue clinical follow-up beyond hospital discharge at any time.

Patients are also informed and asked to give consent to link patient data to existing quality registrations in the Netherlands in order to improve quality of care (the Netherlands Heart Registration (www.nederlandsehartregistratie.nl), the Dutch Hospital Data registration (www.dhd.nl), the Vektis registration (www.vektis.nl) and the NICE registration (www.stichting-nice.nl)). Also, consent to record patient data in the Netherlands Heart Registration is asked in order to answer future scientific issues considering cardiogenic shock.

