9.2 Main analysis of the primary endpoint and ranked secondary endpoints

The following hypotheses are tested in a hierarchical order, to preserve type I error rate:

1. A lower MAP-target regimen (≥ 55 mmHg) is non-inferior to the standard MAP-target regimen ($\text{MAP} \geq 65$ mmHg) in terms of the primary endpoint of the composite of all-cause mortality and severe renal failure at 30 days.
2. A lower MAP-target regimen (≥ 55 mmHg) is superior to the standard MAP-target regimen ($\text{MAP} \geq 65$ mmHg) in terms of the primary endpoint of the composite of all-cause mortality and severe renal failure at 30 days.
3. A lower MAP-target regimen (≥ 55 mmHg) is superior to the standard MAP-target regimen ($\text{MAP} \geq 65$ mmHg) in terms of the first secondary endpoint of all-cause mortality at 30 days.
4. A lower MAP-target regimen (≥ 55 mmHg) is superior to the standard MAP-target regimen ($\text{MAP} \geq 65$ mmHg) in terms of the second secondary endpoint of days alive and out of hospital at 30 days.

All analyses are performed on an intention-to-treat (ITT) basis. The ITT population consists of all subjects who have been randomized (i.e. when the subject number and allocated regimen are recorded in the electronic case report form (eCRF)). Patients are analysed in accordance with the randomized treatment assignment irrespective of the factual implementation of the assigned treatment regimen.

Rates of primary and first secondary endpoint are estimated as the cumulative incidence at 30 days after randomization by the Kaplan-Meier method. Rate differences are defined as the rate in the index group minus the rate in the reference group.

1. Non-inferiority of the lower MAP-target regimen in terms of combined all-cause mortality and severe renal failure at 30 days is declared if the upper limit of the 95% confidence interval (CI) of the rate difference excludes 10%. This is the equivalent of non-inferiority testing with a one-sided alpha of 0.025 with a non-inferiority limit of 10%.
2. Superiority of the lower MAP-target regimen in terms of combined all-cause mortality and severe renal failure at 30 days is declared if the 95% confidence interval (CI) of the rate difference excludes 0%. This is the equivalent of superiority testing with a 2-sided alpha of 0.05.

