9.3 Determination of sample size

The rate of the primary endpoint in the reference group was estimated from the culprit-shock trial, where the event rate was 45.9%.[3] No other study ever tested the same intervention but from experimental myocardial infarction studies we have learned that the administration of noradrenaline is associated with infarct size expansion up to 22%.[12] Besides that, patients with high noradrenaline levels after myocardial infarction have a 4 times higher mortality rate compared with those without high noradrenaline levels.[13] On the basis of the much higher death rate and larger infarct size, we hypothesize that the event rate of the primary endpoint under the lower MAP-target regimen might be 10% lower than that under the standard MAP-target regimen. These assumptions form the basis for the sample size calculation for superiority testing of the primary endpoint. For non-inferiority testing we took a non-inferiority margin of 10%, equivalent to the inverse of the above mentioned treatment benefit.

We calculated that with 752 evaluable patients, the study has 80% power to show superiority of the lower MAP-target regimen (versus the standard MAP-target regimen) under the above mentioned design assumptions, with rates of the primary endpoint of 45.9% under the standard MAP-target regimen and of 35.9% under the lower MAP-target regimen.

We further calculated that with 752 evaluable patients, the study has 79% power to show non-inferiority of the lower MAP-target regimen (versus the standard MAP-target regimen) with a non-inferiority margin of 10% and event rates of the primary endpoint of 45.9% in both treatment regimens.

To allow for attrition rate of 3%, 776 (2 x 388) patients will be randomized.

Sample size calculation is made using PASS Sample Size Software, version 13.

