12.2 Recruitment and consent

Due to the nature of this study population being in imminent danger for death, and the patients often being unconscious, it is not possible to ask the patient or relatives for informed consent before randomization. Therefore, as in previous studies conducted in this population, we will use a “deferred consent” approach. Patients are randomized directly after eligibility has been confirmed. The relatives are informed of the randomization as soon as reasonably possible, by a trained intensive care doctor and/or medical researcher. Consent is asked for continuation of the treatment according to the study protocol. Patients are asked for informed consent when he/she is recovered enough to make a decision. If a patient dies before informed consent of the legal representative has been obtained, data collected during the study may be used without consent. The information and informed consent process and materials are established together with Harteraad (patient and relative association).

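### Deferred-consent rules keep primary endpoint data more readily for patients who die than for survivors, so the 30-day event rates, and the rate difference if refusal differs by arm, can be biased

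*Protocol*

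**What the plan says.** Patients are randomised before consent, and three sections of the Protocol decide which data may then be kept.

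- **Section 5.6.1, representative declines and patient dies:** "if the legal representative(s) declines informed consent and the patient dies, data on the primary endpoint will still be collected". The items named are mortality and RRT.
- **Section 5.6.1, representative declines and patient survives:** consent for further participation "and to use patient data will be asked from the patient once he or she regains consciousness". Nothing is said about endpoint data if that patient then refuses.
- **Section 12.2:** "If a patient dies before informed consent of the legal representative has been obtained, data collected during the study may be used without consent".
- **Section 5.6.2, recovered patient:** "If the patient refuses, no further information beyond hospital discharge is collected".

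The analysis is set out in section 9.2. "The ITT population consists of all subjects who have been randomized", and the rates of the primary and first secondary endpoints "are estimated as the cumulative incidence at 30 days after randomization by the Kaplan-Meier method". The primary endpoint (section 8.1) is death or RRT within 30 days of randomisation. Section 9.3 allows for 3% attrition and does not mention refusal of consent.

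**The concern.** Two patients whose representatives both decline are handled differently according to whether they live. The one who dies stays in the numerator and the denominator. The one who survives stays only by agreeing later. A recovered patient who refuses is followed to discharge, which may come before day 30.

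Kaplan-Meier assumes that patients who leave observation have the same later risk as those who remain. Patients lost because they survived, or censored because they were well enough to go home, probably have lower risk, so both estimated rates tend to rise.

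The comparison between arms is distorted mainly if refusal differs by arm. That is plausible. The trial is open label, and under section 5.6.1 an objection changes treatment only for a patient allocated to the index regimen; reference treatment simply continues. A later analysis plan can model data that were never retained, but cannot recover them.

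**Working it through.** **Inputs from the Protocol.** Section 9.3: event rates 45.9% (reference) and 35.9% (index), margin 10 points, 752 evaluable patients (376 per arm), 776 randomised (388 per arm). Section 9.2: one-sided alpha 0.025 for non-inferiority, two-sided 0.05 for superiority.

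**Reproducing the plan's figures** (normal approximation, unpooled variance, 376 per arm).
- Superiority: SE = √[(0.459×0.541 + 0.359×0.641)/376] = 0.0357. Power = Φ(0.10/0.0357 − 1.96) = 80% (stated: 80%).
- Non-inferiority: SE = √[2×0.459×0.541/376] = 0.0363. Power = Φ(0.10/0.0363 − 1.96) = 79% (stated: 79%).
- Attrition: 752/0.97 = 775.3, rounded up to 776.

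The sample size is not in dispute. With all 388 per arm evaluable, the two powers are 81.3% and 79.8%. These are the baselines below.

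**Assumption.** The Protocol gives no refusal rate. Let r be the share of event-free survivors whose data are affected.

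**Model A, complete loss.** This fits where the representative declines and the surviving patient then declines data use. All events are kept, so the observed rate is p/[p + (1−p)(1−r)].

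*Equal r in both arms:*

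| r | Reference | Index | Difference (points) |
|---|---|---|---|
| 0 | 45.9% | 35.9% | −10.0 |
| 1% | 46.2% | 36.1% | −10.0 |
| 5% | 47.2% | 37.1% | −10.1 |
| 10% | 48.5% | 38.4% | −10.2 |

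The rates move, but the difference hardly does.

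*Index r = 5%, reference 0:*
- True rates 35.9% and 45.9%: index reads 0.359/(0.359 + 0.641×0.95) = 37.1%, so the difference is −8.8 points. Patients lost: 388×0.641×0.05 = 12.4. SE = 0.0355. Superiority power = Φ(0.0881/0.0355 − 1.96) = 70%.
- Both rates truly 45.9%: index reads 47.2%, a spurious +1.3 points. SE = 0.0361. Non-inferiority power = Φ((0.10 − 0.0128)/0.0361 − 1.96) = 68%.

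The 12 patients lost equal the attrition allowance per arm (388 − 376 = 12). That allowance covers the number lost, not the bias.

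*Reference r = 5%, index 0, true excess of 10 points (55.9% against 45.9%):* reference reads 47.2%, so the observed difference is 8.7 points. SE = 0.0360. The chance of a false non-inferiority claim = Φ((0.10 − 0.0872)/0.0360 − 1.96) = 5.4%, against a nominal 2.5%.

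**Model B, censoring at discharge.** This fits a refusal under section 5.6.2. Let e be the share of 30-day events that occur before discharge, assumed 70% to 90% because the Protocol gives no figure. The Kaplan-Meier rate is 1 − (1 − ep) × [1 − (1−e)p / {(1 − ep) − r(1−p)}].

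With p = 0.359, r = 5% in the index arm only, and e = 0.8: 1 − 0.7128 × [1 − 0.0718/(0.7128 − 0.0321)] = 36.2%.

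| e | Index rate read | Bias (points) | Superiority power |
|---|---|---|---|
| 0.7 | 36.4% | +0.5 | 77% |
| 0.8 | 36.2% | +0.3 | 78% |
| 0.9 | 36.1% | +0.2 | 80% |

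With both rates at 45.9% and e = 0.8, the same formula gives 46.3% in the index arm and non-inferiority power of 76%.

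**The case against.** Several points against the concern stand.

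- **Complete loss is the rarer route.** It mainly needs two refusals in series, by the representative and then by the patient. A refusal under section 5.6.2 leaves in-hospital data in place, and Model B shows much less bias. A reader might take the 70% and 68% powers as the expected effect, but they are an upper bound with all loss placed in one arm.
- **Retention after death is not absolute.** A reader might infer that every death is captured. A recovered patient who refuses and dies after discharge but before day 30 is not. Survivors who had RRT are primary events and can also be lost. Both omissions partly offset the upward bias, and Model A ignores them.
- **The likelier imbalance is conservative.** Since an objection changes treatment only in the index arm, excess refusal there is the more natural case. It costs power and does not create false claims. Inflated error requires more loss in the reference arm.
- **Section 9.2 is not contradicted.** A reader might see a conflict with the intention-to-treat definition. That definition says who belongs and how they are grouped; it does not promise complete follow-up, and the attrition allowance anticipates some loss.
- **Retaining data against a competent patient's refusal is for the METC**, and the documents cannot settle it.

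It could also be said that censoring rules belong in the analysis plan. This answers only part of the concern, because sections 5.6.1 and 5.6.2 govern what may be collected and used at all.

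**Conclusion.** The concern holds in limited form. Retention of primary endpoint data depends partly on the outcome, and Kaplan-Meier would treat the resulting loss as uninformative. Both rates tend to be biased upward, with partial offsets. The difference is at risk mainly if refusal differs by arm, which is plausible but not documented.

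At an assumed 5% loss in the index arm alone, the bias runs from about 0.2 to 0.5 points (censoring at discharge, 70% to 90% of events earlier) to 1.2 points (complete loss, upper bound). Superiority power is then 77% to 80%, or 70% at the bound, against 81%. The same imbalance in the reference arm would raise the one-sided non-inferiority error to as much as 5.4%. With equal loss the difference is nearly unbiased.

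This should be fixed, because the remedy is cheap and data not retained cannot be recovered. The documents do not support the stronger conclusion that the primary comparison is invalid as planned.

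**What to change.** 1. Subject to METC agreement, amend sections 5.6.1 and 5.6.2, and align section 12.2, so that one rule for 30-day vital status and RRT applies to every randomised patient, whatever the outcome and whoever declines. Section 5.6.1 already justifies keeping these two items after a death on safety grounds; a safety comparison needs the survivors in the denominator too.
2. Where the METC does not allow this, censor refusing patients at the last date known to be alive and free of RRT. Being alive is not enough, since RRT is itself an event. Keep any RRT already recorded as an event, so far as data use is permitted.
3. Add a sensitivity analysis that counts refusing survivors without known RRT as event-free to day 30, with tipping-point variants by arm.
4. Report refusals by arm and vital status, separating the representative's from the patient's.

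The cost is one consent amendment with ethics review and a small amount of extra analysis. The METC may limit retention for refusing survivors, in which case items 2 to 4 carry the weight.
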